2.1 Primary Variables

The primary variables are related to safety and include the following:

- Ocular and non-ocular treatment-emergent adverse events (TEAE)
- Slit lamp biomicroscopy
- Dilated indirect ophthalmoscopy measures
- Intraocular pressure (IOP), including change from baseline and the proportion of study eyes with an increase from baseline in IOP of 10 mmHg or more and the proportion of study eyes with IOP of 30 mmHg or more.
- Vital signs
- Safety laboratory data

2.2 Secondary Variables

The secondary variables are related to efficacy and include the following:

- BCVA by ETDRS method
- CRT as assessed by SD-OCT
- Area of non-perfusion and area of leakage as assessed by fluorescein angiography (FA) and 3-field fundus photography (FP)
- Percentage of subjects receiving rescue therapy overall

2.3 Exploratory Variables

There are no exploratory variables for this study.

2.4 Statistical Hypotheses

The statistical analysis of primary efficacy variable is conducted to gain information for future studies.

The percentage of study eyes gaining at least 15 letters in BCVA from baseline will be summarized using discrete summary statistics, including exact 90% and 95% confidence intervals (CIs) by treatment group. Treatment group comparisons will be completed using Fisher's exact test.

Treatment group comparisons based on the 90% and 95% CIs using the Farrington-Manning score test will be completed.

$$H_0: p_1 - p_2 = 0$$

$$H_1: p_1 - p_2 \neq 0$$

where H_0 denotes the null hypothesis, and H_1 denotes the alternate hypothesis; p 's denote the proportion of eyes gaining at least 15 letters for each treatment.

3. Study Design and Procedures

3.1 General Study Design

Study visits will be referred to in all tables and listings as the planned study day corresponding to the visit to enable reviewers to understand the assessment timing without referring to the protocol visit schedule. Table 1 shows the scheduled study visits, their planned study day, and the acceptable visit window for each study visit.

Table 1. Scheduled Visits, Study Days, and Visit Windows

Scheduled Visit	Planned Study Day	Visit Window
Visit 1		N/A
Visit 2		N/A
Visit 3		± 2 Days
		± 2 Days
Visit 4		± 3 Days
Visit 5		± 3 Days
Visit 6		± 3 Days
Visit 7		± 3 Days
Visit 8		± 3 Days
Visit 9		± 3 Days
Visit 10		± 3 Days
Visit 11		± 3 Days
Visit 12		± 3 Days

3.2 Schedule of Visits and Assessments

The schedule of visits and assessments is provided on Table 2.

Table 2. Schedule of Visits and Procedures.

Procedure	Screening ¹	Baseline/ Treatment	Initial Phase		Follow-Up Period ¹ (Randomized Phase)						Implant Observation Period ² (if required)		
	V1 to -1	V2	V3 ³ (± 2 days)	V3b ³ (± 2 days)	V4 (± 3 days)	V5 (± 3 days)	V6 (± 3 days)	V7 (± 3 days)	V8 (± 3 days)	V9 (± 3 days)	V10 (± 3 days)	V11 (± 3 days)	V12 (± 3 days)
Informed consent review	X												
Demographics/ medical & ocular history ⁵	X												
Concomitant medication query	X	X	X	X	X	X	X	X	X	X	X	X	X
Adverse events query		X	X	X	X	X	X	X	X	X	X	X	X
BCVA – (ETDRS)	X	X	X	X	X	X	X	X	X	X	X	X	X
Slit-lamp biomicroscopy	X	X	X	X	X	X	X	X	X	X	X	X	X
Gonioscopy*	X	X					X*			X*			
IOP check	X	X	X	X	X	X	X	X	X	X	X	X	X
Posterior segment OCT*	X	X			X*	X*	X*	X*	X*	X*	X*	X*	X*
Fluorescein Angiography	X	X					X			X			
3-Field fundus photography*	X	X					X*			X*	X*	X*	X*
Dilated fundus exam*	X	X	X	X	X	X	X*	X	X	X*	X*	X*	X*
Vitreous implant residual assessment*			X*	X*	X*	X*	X*	X*	X*	X*	X*	X*	X*
Vital signs	X	X	X	X	X	X	X	X	X	X	X	X	X
Laboratory tests	X				X	X				X			
Pregnancy test	X									X			
Treatment ⁶		X											

¹ Screening and post-implant treatment schedule applies to both Cohorts.

² Implant observation period should continue for any individual subject as long as residual implant is visible, or to [REDACTED] whichever comes first.

³ [REDACTED]

⁴ An interim database lock may be conducted when the first 20 subjects have completed their [REDACTED] visit.

⁵ [REDACTED]

⁶ [REDACTED]

* Assessments performed in study eye only at these visits.

4. Study Treatments

4.1 Method of Assigning Subjects to Treatment Groups

Providing none of the subjects experience any clinically-meaningful ocular adverse reactions (possibly) related to treatment with AR-1105 during the initial phase, the study will continue into the randomized phase. During the randomized phase of the study, subjects will be assigned in a 1:1 ratio to either AR-1105-CF1 or AR-1105-CF2.

5. Sample Size and Power Considerations

This study is not powered to detect a pre-stated efficacy signal, but rather will be used to inform the design and power for future studies. With a sample size of 20 evaluable subjects per treatment group, the study will have 95% confidence of ruling out adverse events (AE) with true incidence rates of 13.9% or higher within each treatment group. That is, with 20 subjects in a treatment group, if an AE of a specific type is not observed, then with 95% confidence, the true incidence rate of that AE is less than 13.9%.

6. Data Preparation

All reported study data will be recorded on the electronic case report forms (eCRF) supplied by Statistic & Data Corporation (SDC). Only the Principal Investigator and authorized study staff according to the Delegation of Responsibilities log are entitled to make entries in the eCRF.

After data are entered into the clinical study database, electronic edit checks and data review will be performed. All data validation specifications and procedures are detailed in the Data Validation Manual as a separate document. When the database has been declared to be complete and accurate, the database will be locked. Any changes to the database after data have been locked can only be made with the approval of the Sponsor and Trial Runners in consultation with SDC.

The final analyses outlined in this document will be carried out after the following have occurred:

- All data management requirements are met according to SDC standard operating procedures, including data entry, performance of edit and validation checks, documentation and resolution of data queries, and database lock with written authorization provided by appropriate SDC and Sponsor personnel.
- Protocol deviations have been identified and status defined (major/minor deviations).
- Analysis populations have been determined.

7. Analysis Populations

7.1 Safety

The safety population will include all subjects who received study medication. This population will be used to summarize safety variables and will summarize subjects as treated.

7.2 Intent-to-Treat

The intent-to-treat (ITT) population will include all subjects who received study medication. This population will be the primary population for efficacy analyses and will be used to summarize all efficacy variables and will summarize subjects as treated.

7.3 Per Protocol

The per protocol (PP) population is a subset of the ITT population, which will include those subjects who do not have major protocol violations likely to seriously affect the efficacy outcomes of the study. This population will be the secondary population for efficacy analyses and will be used to summarize a subset of efficacy variables as needed. If the PP and ITT populations are exactly the same, then additional efficacy analyses on the PP population will not be performed. The PP population will summarize subjects as treated.

8. General Statistical Considerations

8.1 Unit of Analysis

The unit of analysis in this study will be the study eye (see Protocol Section 4.2 for details on selection of study eye) for all efficacy, and study eye and subject for safety summaries. Additionally, non-ocular AEs and medical history (ocular and non-ocular) will be presented at the subject level. Fellow eye safety summaries will also be presented as appropriate.

8.2 Missing or Inconclusive Data Handling

8.2.1 MISSING/PARTIAL DATES FOR AEs

Missing/Partial AE start dates will be imputed as follows. The original dates will be displayed in data listings and the imputed dates will be used in derivations only for study day and TEAEs.

- Dates with missing day only will be imputed as the 1st of the month unless the month and year are the same as the month and year of the first exposure to treatment, in which case the missing day will be imputed as the first exposure to treatment day.
- Dates with both day and month missing will be imputed as 1 Jan unless the year is same as the year of first exposure to treatment, in which case missing day and month will be imputed as the first exposure to treatment day and month.
- A completely missing date will be imputed as the first exposure to treatment unless the AE end date is on or before the first exposure to treatment, in which case the missing date will be imputed as 1 Jan of the same year as the end date.

Missing/Partial AE end dates will be imputed as follows:

- Dates with missing day only will be imputed as the last day of the month.
- Dates with both day and month missing will be imputed as 31 Dec.
- Complete missing dates will not be imputed.

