5.3 Selection and Timing of Dose for Each Patient

A single intravitreal injection (with 2 implants) will be given on Day 1.

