8.2.2 MISSING/PARTIAL DATES FOR CONCOMITANT MEDICATIONS

Missing/Partial start dates for concomitant medications will be imputed as follows. The original dates will be displayed in data listings and the imputed dates will be used in derivations only for the differentiation of prior and/or concomitant medications.

- Dates with missing day only will be imputed as the 1st of the month unless the month and year are the same as the month and year of the first exposure to treatment, in which case the missing day will be imputed as the first exposure to treatment day.
- Dates with both day and month missing will be imputed as 1 Jan unless the year is same as the year of first exposure to treatment, in which case missing day and month will be imputed as the first exposure to treatment day and month.
- A completely missing date will be imputed as the first exposure to treatment unless the concomitant medication end date is on or before the first dose date of study medication, in which case the missing date will be imputed as 1 Jan of the same year as the end date.

Missing/Partial end dates for concomitant medications will be imputed as follows:

- Dates with missing day only will be imputed as the last day of the month unless the month and year are the same as month and year of the last exposure to treatment, in which case missing day will be imputed as the last exposure to treatment day.
- Dates with both day and month missing will be imputed as 31 Dec unless the the year is the same as the year of the last exposure to treatment, in which case missing day and month will be imputed as the last exposure to treatment day and month.

- Complete missing dates will not be imputed.

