11.2 Prior and Concomitant Medications

Prior and concomitant medications will be coded using World Health Organization (WHO) Drug Dictionary (WHODrug Global B3, September 2018) and summarized to the therapeutic drug class (Anatomical Therapeutic Chemical [ATC] 4 classification) and preferred name. If the ATC 4 classification is not provided, the next lowest classification that is provided in the coding dictionary will be used. The preferred name will be defined as the active ingredient; if the active ingredient is not provided or includes more than two ingredients (e.g., multivitamins), then the drug name will be summarized as the preferred name.

Concomitant medications are defined as those medications listed as having been taken (1) prior to initiation of study medication administration and continuing for any period of time following the first administration of study medication or (2) at any time following the first administration of study medication.

Prior and concomitant medications will be summarized for all subjects. Medications will be tabulated for each treatment group using frequencies and percentages. Subjects may have more than 1 medication per ATC text. At each level of subject summarization, a subject will be counted once if he/she reports 1 or more medications. Percentages will be based on the number of subjects in each treatment group. Listings of prior and concomitant medications will be generated for ocular and non-ocular data.

12. Implant Residual Assessment

Duration of implant visibility in days will be calculated as: (End Date - Date of Implant Injection) + 1, where the end date is defined as the latest date at which the implant is visible or date of implant injection for subjects whose implants are not visible at any of the follow up visits. Vitreous implant visualization will also be summarized at each visit by treatment group using categorical statistics. A subject listing will be provided for vitreous implant residual assessment.

13. Efficacy Analyses

The efficacy analyses will include the following:

- Percentage of subjects with ≥ 15 -letter improvement compared to baseline BCVA (assessed by ETDRS) at Month 6.
- Change from baseline in CRT as assessed by SD-OCT at Months 1, 2, 3, 4, 5, and 6
- Change from baseline BCVA letter score at Months 1, 2, 3, 4, 5, and 6
- Percentage of subjects with a ≥ 10 -letter improvement compared to baseline BCVA at Months 1, 2, 3, 4, 5, and 6

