15.1 Adverse Events

An AE is defined as any untoward medical occurrence associated with the use of a drug in humans, whether or not the event is considered drug-related. An AE can therefore be any unfavorable and unintended sign (e.g., an abnormal laboratory finding), symptom, or disease occurring after informed consent form is signed and dated, without any judgment about causality. Any pre-existing medical condition that worsens after first administration of the study medication will also be considered a new AE. The AE reporting period starts from the time the subject signs and dates the informed consent and until 30 days after the subject's last study visit. All Aes will be coded using the MedDRA 21.1.

Treatment-emergent adverse events are defined as any event that occurs or worsens on or after the study treatment is initiated. Adverse events recorded in the eCRF which began prior to treatment will not be included in the summary tables but will be included in the AE data listings.

An overall summary will be presented that includes the number of TEAEs and the number and percentage of subjects who experienced at least one TEAE, by treatment group. This summary will also include breakdowns of TEAEs further categorized as ocular (study eye, fellow eye, and both eyes separately) or non-ocular, serious TEAEs, TEAEs by maximum severity, TEAEs by maximum relationship to study medication, TEAEs by maximum relationship to study procedure, TEAEs by maximum expectedness, number of serious TEAEs, number of subjects with any serious TEAEs, and with TEAEs leading to death.

Additional summaries of TEAEs will be provided showing the number and percentage of subjects who experienced at least one TEAE. These summaries will be presented by system organ class (SOC) and preferred term (PT). Non-ocular TEAEs will be summarized using discrete summary statistics and presented by treatment group at the subject level by SOC and PT. Ocular TEAEs will be similarly summarized at the subject level for study eyes, fellow eyes, and both eyes separately. If a subject reports the same PT multiple times within the same SOC, that PT will only be reported once within that SOC. As with the PT, if a subject reports multiple conditions within the same SOC, that SOC will only be reported once. In the summary, SOC will be listed in ascending alphabetical order; PTs will be listed in order of descending frequency for all subjects within each SOC.

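### Partial AE start dates are set to the injection date without checking the AE end date, so an event that ended before injection can count as treatment-emergent

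*SAP*

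**What the plan says.** **AE start dates.** SAP 8.2.1 has three rules.

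- Day missing: first of the month, unless month and year match the injection, "in which case the missing day will be imputed as the first exposure to treatment day".
- Day and month missing: 1 January, unless the year matches the injection, "in which case missing day and month will be imputed as the first exposure to treatment day and month".
- Whole date missing: "A completely missing date will be imputed as the first exposure to treatment unless the AE end date is on or before the first exposure". In that exception the start becomes 1 January of the end-date year.

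Only the third rule looks at the end date. The section also says that "the imputed dates will be used in derivations only for study day and TEAEs".

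**What counts as a TEAE.** SAP 15.1: "Treatment-emergent adverse events are defined as any event that occurs or worsens on or after the study treatment is initiated". The same section keeps AEs that began before treatment out of the summary tables and shows them only in the listings. AE collection starts at consent (Protocol 6.8, SAP 15.1). The Protocol's contents entry for Section 7.1 puts screening at Day -28 to -1.

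**Medication end dates.** SAP 8.2.2 sends a partial end date to the end of the month or year, unless it falls in the month of last exposure, "in which case missing day will be imputed as the last exposure to treatment day". A parallel exception covers a missing day and month in the year of last exposure. Protocol 5.3 gives one dose: "A single intravitreal injection (with 2 implants) will be given on Day 1".

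**The concern.** The SAP recognises that an AE with a known early end cannot have started at injection, but guards only the least informative case. A start known to the month or year is handled worse than a start that is wholly unknown. The resulting record is impossible, with onset after resolution, and it enters the TEAE tables against SAP 15.1.

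TEAEs are among the primary safety variables (SAP 2.1), and arms have about 20 subjects, so a single misplaced event is visible in a table.

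For medications, an exception keyed to last exposure suits repeated dosing. Here first and last exposure are the same day, so the exception pulls end dates back to Day 1 and can place them before the drug was started.

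**Working it through.** The point concerns derivation rules, and the plan gives no figure for it. The nearest is the sample-size statement, which reproduces: 1 − 0.05^(1/20) = 0.139, or 13.9%. It describes an AE type with no events among 20 subjects.

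**Step 1: AE start rules applied literally.** Illustrative injection 20 March 2019; known AE end 10 March 2019.

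| Recorded start | Rule applied | Imputed start | After the end? | TEAE? |
|---|---|---|---|---|
| Day unknown, March 2019 | injection day | 20 March 2019 | yes, by 10 days | yes |
| Day and month unknown, 2019 | injection day and month | 20 March 2019 | yes, by 10 days | yes |
| Wholly unknown | end-date exception | 1 January 2019 | no | no |

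**Step 2: the same event with the exception extended.** The end of 10 March is on or before 20 March, so the first two rows become 1 March and 1 January 2019. Both precede the end and neither is a TEAE.

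**Step 3: how often the rule misfires, given such a record.** The documents give no rate of partial dates, so this is conditional and rests on assumptions: injection dates uniform over 2019, AE onset uniform over the 28 days before injection, exact end date known and before injection. For a one-day AE there are 365 × 28 = 10,220 date pairs.

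- Day missing: the rule misfires when onset falls in the injection month. Pairs per month are 462 (31-day months), 434 (30-day) and 378 (February), so 7 × 462 + 4 × 434 + 378 = 5,348, and 5,348 / 10,220 = 52%.
- Day and month missing: the rule misfires unless onset falls in the previous year. That excludes 28 + 27 + … + 1 = 406 pairs, and 1 − 406 / 10,220 = 96%.

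For AEs of 3 and 7 days the figures are 49% and 42% (day missing) and 96% and 95% (day and month missing). These are shares of partial-date AEs that ended before injection, not of all AEs.

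**Step 4: effect on a table.** One false case in a subject who does not otherwise have the term adds 1/20 = 5 percentage points in an arm of 20.

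**Step 5: medication end dates.** Same injection date, so last exposure = Day 1 = 20 March 2019.

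| Start | Recorded end | End under SAP 8.2.2 | End under the AE end-date rule |
|---|---|---|---|
| 21 March 2019 | day unknown, March 2019 | 20 March, 1 day before start | 31 March 2019 |
| 10 June 2019 | day and month unknown, 2019 | 20 March, 82 days before start (11 + 30 + 31 + 10) | 31 December 2019 |
| 1 January 2019 | day unknown, March 2019 | 20 March = Day 1 | 31 March 2019 |

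The first two drugs are concomitant by their start dates whatever end is imputed. Only in the third does the imputation bear on the label, because SAP 11.2 asks whether the drug was "continuing for any period of time following the first administration of study medication" and does not say how an end on Day 1 is classed.

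**The case against.** **Setting a partial start to Day 1 is standard and conservative.** This stands when the end date is missing or after injection, since the event may then have begun after treatment. It does not cover an event known to have ended earlier.

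**Such records will be rare.** This also stands. Screening is short, Protocol 6.8 asks for start and stop dates, and edit checks and queries precede lock (Protocol 10.12, SAP 6). But the imputation rules exist for dates that stay unresolved, so they should be right for those.

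**SAP 15.1 already excludes AEs that began before treatment.** It does, and so the SAP contradicts itself for these records: 8.2.1 supplies a start date that makes the event treatment-emergent.

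Three stronger readings are tempting and not supported.

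- A reader might infer that steroids or IOP-lowering drugs given after injection would be labelled prior-only. A drug with a known start after injection is concomitant under the second limb of SAP 11.2. Imputed medication dates serve only that label, listings show the original dates, and the planned medication tables (14.1.4.1 and 14.1.4.2) combine prior and concomitant use. A drug with no end date is left alone, because wholly missing end dates are not imputed.
- A reader might infer that one false event loosens a reported upper confidence bound. The 13.9% is a planning statement for zero events; SAP 15.1 plans counts and percentages for TEAEs, without bounds.
- A reader might infer that a safety signal could be hidden. The AE error only adds events, and the same rule applies in both arms.

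**Conclusion.** The AE part holds as a narrow rule defect. It needs a partial start date in the injection month or year together with an end date known to precede injection. Such a record gets an onset after its own end and is counted as a TEAE, contrary to SAP 15.1. The number of such records is not given and is probably small. The direction is towards overstated TEAE incidence, by 5 percentage points per false case for a term in an arm of 20. The misfire shares of 42% to 52% and 95% to 96% depend on the uniform-date assumptions stated with them.

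The medication part is secondary. The exceptions are misfitted to a single-injection trial and can give an end before a start. They can affect only the prior/concomitant label of drugs started before injection with a partial end date in the injection month or year, and change little or nothing in the planned tables.

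This is a minor correction to make before database lock. It does not threaten the trial's conclusions.

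**What to change.** **SAP 8.2.1.** Add the exception already written for wholly missing starts to both partial-start rules. If the AE end date is on or before first exposure, impute the first of the known month, or 1 January of the known year. Keep the on-or-before cut-off identical across the three rules; otherwise an AE ending on Day 1 would be classed differently according to how much of its start date is missing. Add one line requiring that an imputed start is never later than the end date.

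**SAP 8.2.2.** Delete the two last-exposure exceptions for medication end dates. Use the last day of the month or 31 December, as SAP 8.2.1 already does for AE end dates.

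**Cost.** A few sentences of SAP text and a small change to the date-derivation program. No new data are needed, and few records should change.
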